7.2 Clinical Evaluation

The clinical laboratory at Universite des Sciences, Techniques, et Technologies de Bamako (USTTB) will perform routine CBCs with differential and platelet counts.

7.3 Laboratory Evaluation

In an exploratory analysis, the levels of multiple cytokines will be measured in plasma using a LUMINEX assay platform. Cytokines will include (but may not be limited to) those we previously found to be up-regulated in response to malaria (47): IL-4, IL-6, IL-10, IL-12, IFN-γ, and TNF.

8 POTENTIAL RISKS AND BENEFITS

8.1 Potential Risks

Potential risks to participants are associated with the following procedures:

Venipuncture and finger sticks. Risks occasionally associated with venipuncture include pain, bruising, bleeding, and infection at the site of venipuncture, lightheadedness, and rarely, syncope.

Indwelling venous catheterization. Risks rarely associated with the placement of indwelling venous catheters include line infection and venous thrombosis.

If the IV line becomes compromised and cannot be replaced, treatment will be continued with intramuscular artemether. In rare circumstances, intramuscular injection may cause infection of superficial and deep tissues, including muscle abscess. Inappropriate injection techniques may result in nerve damage that may be permanent.

Drug administration. Expected AEs of drugs used in this study are generally mild in nature and not treatment-limiting.

Repeat dosing of oAC may cause constipation, and stools may be blackened. Aspiration of oAC in patients who vomit has been reported to produce airway obstruction (which is one reason why children presenting with repeated vomiting will not be eligible). oAC can reduce the absorption of other oral medications for as long as it is present in the intestines. The effect is greatest when oAC is given simultaneously (i.e., within 1 h) with other oral medication, additional doses of which may be required to obtain the same clinical effect.

Gastrointestinal effects (nausea, vomiting, diarrhea, abdominal discomfort) have been noted with AQ treatment, but have been extremely uncommon in our study population in the past 5 years. Rarely, itching and skin rash may occur.

No AEs are expected from AS or artemether treatment. The drugs are well tolerated, and there are no known common side effects. Rarely, allergic reactions and skin rash have been described.

Study participants will be made fully aware that this is the first time that patients with malaria will receive adjunct treatment with oAC. While there is currently no evidence that oAC might do any harm, we cannot exclude the theoretical possibility that oAC may produce unexpected, less desirable outcomes.

Coartem is now widely used for the treatment of acute uncomplicated malaria in many African countries. In 10% of patients, Coartem may cause headache, dizziness, abdominal pain and loss of appetite. In 1-10% of patients, Coartem may cause insomnia, palpitations, nausea, vomiting, diarrhea, itchiness, skin rash, cough, myalgias, arthralgias and malaise.

8.2 Potential Benefits

Children that participate in this study will directly benefit from malaria diagnosis and treatment. Study participants will be made aware that IV administration of AS is not the standard of care for UM and that the malaria episode can be treated equally well with oral ACTs that will be provided to the child in case the caregiver chooses for the child not to participate in this study. Information gained from this study might contribute to the development of a safe and effective adjunct treatment to prevent the development of SM or lessen the morbidity and mortality of SM. The alternative to participating in this study is to not participate.

9 ASSESSMENT OF SAFETY AND ADVERSE EVENT REPORTING PLAN

9.1 Definitions

AE: Any untoward or unfavorable medical occurrence in a human subject, including any abnormal sign (e.g., abnormal physical exam or laboratory data), symptom, or disease, which is temporally associated with the subject's participation in the research, whether or not it is considered related to the research.

SAE: Any AE that

- results in death;
- is life-threatening (places subject at immediate risk of death from event as it occurs);
- results in inpatient hospitalization or prolongation of existing hospitalization;
- results in a persistent or significant incapacity or substantial disruption of the ability to conduct normal life functions;
- results in a congenital anomaly/birth defect; or
- based upon appropriate medical judgment, may jeopardize the subject's health and may require medical or surgical intervention to prevent one of the other outcomes listed in this definition.

Unanticipated Problem that is not an Adverse Event (UPnonAE): Any unanticipated problem that does not fit the definition of an AE but which may, in the opinion of the investigator, involve risk to the subject, affect others in the research study, or significantly impact the integrity of research data, for example, occurrences of breaches of confidentiality, accidental destruction of study records, or unaccounted-for study drug will be reported.

Protocol Violation: Any change, divergence, or departure from the study procedures in an Institutional Review Board (IRB)-approved research protocol that has a major impact on the subject's rights, safety, or well-being, and/or the completeness, accuracy, or reliability of the study data.

Protocol Deviation: Any change, divergence, or departure from the IRB-approved study procedures in a research protocol that does not have a major impact on the subject's rights, safety or well-being, or the completeness, accuracy, and reliability of study data.

Unanticipated Problem: Any incident, experience, or outcome that is

- 1. unexpected in terms of nature, severity, or frequency in relation to
 - a. the research risks described in the IRB-approved protocol and ICF, or other study documents; and
 - b. the characteristics of the subject population being studied; and
- 2. related or possibly related to participation in the research; and
- 3. places subjects or others at a greater risk of harm (including physical, psychological, economic, or social harm) than was previously known or recognized.

9.2 Recording/Documentation

AEs discovered by appropriate questioning and examination will be recorded in the AE section of the CRF. Mild or moderate events that are reasonably expected in this study (symptoms of malaria such as fever, myalgias, arthralgias, anorexia, nausea, and malaise) will be recorded in the Review of Symptoms section of the CRF. Source documents will include progress notes and laboratory reports.

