We will hospitalize children for 48 h to monitor their clinical status and IV catheter, and ensure the accurate timing of blood sampling. Vital signs, state of consciousness, and selected symptoms (nausea, vomiting, diarrhea, constipation, abdominal pain, headache, and dizziness) will be monitored at 0, 2, 4, 6, 8, and 12 h, and then every 6 h until 48 hours or until parasitemia is undetectable (one negative thick blood film), whichever is later. Finger-prick blood samples will be obtained at 0, 2, 4, 6, 8, and 12 h, and then every 6 h until parasitemia is undetectable. In

Kenieroba, we previously found that 7%, 13%, 34%, 28%, 16%, and 2% of children aged 2-10 years (n=160) cleared their parasitemia by 12, 18, 24, 30, 36, and 42 h, respectively (38). We therefore expect that finger-prick blood sampling will be completed within 48 h for all children.

We will obtain 3 mL venous blood at 0, 24, and 48 h to perform a complete blood count (CBC) with differential and platelet counts, preserve RNA, and store plasma for research purposes. Transcriptional profiles and plasma cytokine levels in children with UM children will later be compared to those with SM.

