4.4 Subject Inclusion/Exclusion Criteria

4.4.1 Inclusion Criteria

- 1. Age 2 to 10 years, inclusive
- 2. Resident of Kenieroba
- 3. Uncomplicated malaria*
- 4. *P. falciparum* density 10,000–70,000/µL, inclusive
- 5. Willingness to participate in the study as evidenced by informed consent of the child's parent or guardian
- 6. Ability to swallow oral medication

*Uncomplicated malaria: axillary temperature >37.5°C *or* history of fever in the past few days *and* no criteria of SM (see next paragraph) *and* no other etiologies of febrile illness (e.g., respiratory tract infection) on clinical examination.

Severe *P. falciparum* malaria: parasitemia of any density *and* any one of the following: coma (Blantyre coma score ≤ 2), convulsions (witnessed by investigator), severe prostration, severe anemia (hemoglobin ≤ 6 g/dl), respiratory distress, hypoglycemia (serum glucose ≤ 40 mg/dl), jaundice/icterus, shock (systolic blood pressure ≤ 70 mmHg, rapid pulse, cool extremities), cessation of eating and drinking, repetitive vomiting.

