6.2 Analysis plan

Analysis of safety data:

The local reactogenicity at the site where the IV catheter is placed will be assessed using the grading scale provided in Appendix 5, which is based on the FDA toxicity grading scale for healthy adults and adolescents.

Descriptive summaries of the frequency and (where applicable) duration of systemic signs and symptoms such as nausea, vomiting, diarrhea, abdominal pain, headache, and dizziness will be provided for each group.

Clinical and laboratory assessments resulting in numerical values (pulse, blood pressure, respiratory rate, state of consciousness assessed by the Blantyre coma score, axillary temperature, white blood cell counts, hemoglobin, and platelet counts) will be compared at each time-point between groups in light of age-specific normal values available for African pediatric populations (44-46).

It is expected that all the above listed parameters will be influenced to various degrees by the malaria parasite infection itself, and most of the systemic signs or symptoms are also listed as

common side effects of the antimalarial drugs used to treat the infection. Therefore, it won't be possible to establish the relatedness of any such findings to either the parasite infection, or any of the study-related interventions. For that reason, we will limit our analysis to a comparison of the frequency and duration (or, for numeric parameters the level) of such findings between both groups. This will enable us to determine whether adjunct treatment with oAC significantly alters the clinical course of disease, or whether the safety of IV AS is compromised by adding oAC.

Analysis of parasite clearance data:

Parasite clearance will be calculated for each participant as previously described (38), and compared between groups using a one sided test with a 2.5% significance level. The hypotheses are: H_0 : T_H for AS + oAC – AS >25.57 min and H_1 : T_H for AS + oAC – AS <25.57 min. The Welch's t-test will be performed and its associated 95% CI will be calculated for the mean difference between AS+oAC – AS. If the upper limit of this interval is <25.57 min, then the null hypothesis will be rejected and non-inferiority will be demonstrated.

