7 STUDY PROCEDURES AND EVALUATION

7.1 Detailed Study Procedure Schedule

0 hours

- 1. Verify that informed consent was obtained.
- 2. Ensure that all inclusion/exclusion criteria are met.
- 3. Measure child's weight and vital signs: axillary temperature, blood pressure, heart and breathing rates, and state of consciousness.
- 4. Perform abbreviated history and physical examination and review for specific symptoms (i.e., nausea, vomiting, diarrhea, constipation, abdominal pain, headache, dizziness).
- 5. Place IV catheter in the arm.
- 6. Obtain 3 mL blood via IV catheter for research purposes: CBC with differential and platelet count, RNA preservation, and plasma preparation.
- 7. Prepare thick/thin blood films from finger-prick blood sample, count parasite density. Slide readers will be blinded to study participant's group allocation.
- 8. Administer AS 2.4 mg/kg IV to all children.
- 9. Administer a weight-based dose of Actidose Aqua® to children in the AS+oAC group, and a weight-based volume of clean water to children in the AS group.

2 hours (±10 min)

- 1. Prepare thick and thin blood films and count parasite density. Slide readers will be blinded to study participant's group allocation.
- 2. Measure vital signs, assess consciousness, and review specific symptoms (i.e., nausea, vomiting, diarrhea, constipation, abdominal pain, headache, dizziness).

4 hours (±10 min)

- 1. Prepare thick and thin blood films and count parasite density. Slide readers will be blinded to study participant's group allocation.
- 2. Measure vital signs, assess consciousness, and review specific symptoms. (i.e., nausea, vomiting, diarrhea, constipation, abdominal pain, headache, dizziness)

6 hours (±10 min)

- 1. Prepare thick and thin blood films and count parasite density. Slide readers will be blinded to study participant's group allocation.
- 2. Measure vital signs, assess consciousness, and review specific symptoms. (i.e., nausea, vomiting, diarrhea, constipation, abdominal pain, headache, dizziness)
- 3. Administer a weight-based dose of Actidose Aqua® to children in the AS+oAC group, and a weight-based volume of clean water to children in the AS group.

8 hours (±10 min)

- 1. Prepare thick and thin blood films and count parasite density. Slide readers will be blinded to study participant's group allocation.

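### Four of the six expected malaria symptoms named in Section 9.2 are not prompted by the symptom review meant to record them, so they may be captured incompletely and unevenly by arm

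*Combined protocol and SAP*

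**What the plan says.** Section 9.1 defines an AE broadly, as an untoward occurrence "temporally associated with the subject's participation in the research, whether or not it is considered related to the research". Section 9.2 then divides the recording. AEs found on questioning and examination go in the AE section of the CRF, but "Mild or moderate events that are reasonably expected in this study (symptoms of malaria such as fever, myalgias, arthralgias, anorexia, nausea, and malaise" are listed separately, and these "will be recorded in the Review of Symptoms section of the CRF".

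Two sections describe what is asked. Section 3.2 says that "selected symptoms (nausea, vomiting, diarrhea, constipation, abdominal pain, headache, and dizziness) will be monitored", at 0, 2, 4, 6, 8 and 12 h and then six-hourly to at least 48 h. Section 7.1 gives the same seven at 0 h, "review for specific symptoms (i.e., nausea, vomiting, diarrhea, constipation, abdominal pain, headache, dizziness", and repeats them at each inpatient time point. Temperature is taken at the same visits, among the "vital signs: axillary temperature, blood pressure, heart and breathing rates, and state of consciousness". For the 168 h visit, Section 7.1 refers to a review of specific symptoms without listing them again.

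Section 6.2 plans descriptive summaries of the frequency and, where applicable, duration of systemic signs and symptoms by group. It gives examples, all of them from the prompted list. It also states that "it won't be possible to establish the relatedness of any such findings to either the parasite infection, or any of the study-related interventions", and for that reason confines the analysis to between-group comparison. Section 6.3.1 lists safety of oAC first under Primary Outcome.

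**The concern.** The section that says where expected symptoms are recorded and the sections that say what is asked do not match. Section 9.2 makes the Review of Symptoms the record for six named examples, but most of them are not among the symptoms the review asks about. An unprompted symptom is recorded only if a child aged 2 to 10 or a caregiver mentions it, or if staff notice it.

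The trial is open-label, and only the slide readers are stated to be blinded. Section 3.2 accepts the lack of blinding because parasite clearance is objective. That reasoning does not extend to reported symptoms. Children, caregivers and ward staff can all tell charcoal from water, and what is volunteered or noticed may depend on that. At stake is the by-arm comparison of frequency and duration in 6.2. Duration is the more exposed of the two, because it needs the same question asked at successive visits.

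**Working it through.** No figure in the plan depends on this point, so the check compares the sections.

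**Step 1: the six symptoms named in 9.2 against what is prompted or measured in 3.2 and 7.1.**

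| Named in 9.2 | On the seven-symptom list | Measured otherwise |
|---|---|---|
| Nausea | Yes | – |
| Fever | No | Yes, axillary temperature |
| Myalgia | No | No |
| Arthralgia | No | No |
| Anorexia | No | No |
| Malaise | No | No |

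Against the symptom list alone, 6 − 1 = 5 are not prompted. Counting the temperature reading as capture of fever, 5 − 1 = 4 remain.

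**Step 2: how often they go unprompted.** The scheduled inpatient reviews are at 0, 2, 4, 6, 8, 12, 18, 24, 30, 36, 42 and 48 h, which makes 12. For each child, 4 symptoms × 12 reviews = 48 symptom checks are not prompted. With 35 children per arm completing the schedule, that is 35 × 48 = 1,680 per arm. The 0 h review precedes the first dose, so 11 of the 12 come after treatment has started. The 168 h visit is left out of the count because its symptom list is not spelled out.

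**Step 3: what 6.2 needs.** Frequency and duration by arm require the same ascertainment in both arms, starting from a baseline. For the seven prompted symptoms and temperature, the schedule provides this. For the other four it does not. The examples in 6.2 are open-ended, so these four are within its scope although none is named there.

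**Step 4: where the counts come from.** Section 9.2 places mild or moderate expected symptoms in one CRF section and leaves more severe ones to the other. One symptom can therefore sit in either place, depending on its grade. Section 6.2 does not say which section supplies the frequencies. A count from only one of them would be partial.

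**The case against.** The strongest reply is that nothing is missing. Section 9.2 says these events are to be recorded, and it names progress notes among the source documents. It also expects AEs to be sought by questioning and examination, and 7.1 includes an abbreviated history at 0 h. The CRF is not in the documents and may have fields for the four symptoms. This part stands: a reader might infer that the events are lost or appear in neither record, and the text does not support that. What the reply does not supply is a scheduled question, put the same way to both arms.

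A reader might also infer that the routing rule itself creates an arm difference in AE counts, with the same nausea labelled as malaria in one arm and as an AE in the other. The documents do not support this either. Nausea is a named example, so at mild or moderate grade it goes to the same place in both arms and is prompted at every inpatient review. Section 6.2 compares findings irrespective of attribution and plans no comparison of AE counts. Any worked example of relabelling would rest on invented rates and touch no planned analysis.

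A third inference is that anorexia is critical because "cessation of eating and drinking, repetitive vomiting" are among the protocol's criteria for severe malaria. Section 9.2 diverts only mild or moderate events, so anorexia at that level falls outside the diversion. Section 8.1 does not list reduced appetite as a risk of oAC, and controls drink an equivalent volume of water.

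Finally, the oAC effects that the protocol does foresee are largely covered. Constipation and vomiting are prompted, and passage of stool is recorded on each AQ day. This limits the importance of the gap but does not close it: 6.2 aims to show whether oAC alters the clinical course of disease, which is wider than its known side effects.

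**Conclusion.** The point holds as a mismatch in ascertainment. Four of the six symptoms that 9.2 assigns to the Review of Symptoms are not prompted at any of the 12 reviews from 0 to 48 h. The likely result is incomplete capture, possibly uneven by arm, and a weaker comparison in 6.2 for those four symptoms only. Nausea, fever and the other six prompted symptoms are collected on the same schedule in both arms.

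This rests on two assumptions: that the CRF follows the seven-symptom list in 3.2 and 7.1, and that unprompted reporting is less complete than prompted reporting. The size and direction of any arm difference cannot be estimated, because the documents give neither symptom rates nor reporting rates. The parasite half-life comparison, its margin and the 35 per group are not affected. This is a low-cost improvement and not a fault that undermines the trial.

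**What to change.** 1. Add myalgia, arthralgia, anorexia and malaise to the symptom review in 3.2 and 7.1, asked in the same words in both arms at every scheduled review including 0 h. State that the 168 h review uses the same list.
2. State in 6.2 that by-arm symptom frequencies are counted from the Review of Symptoms together with any AE-section entries for the same symptoms, each event counted once, whatever its presumed cause. There is no need to enter every symptom in both CRF sections: under the definition in 9.1 that would only duplicate records.

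The cost is four short questions per review (48 per child over the 12 inpatient reviews), a small CRF change, a sentence in 6.2 and slightly more recorded events. For the youngest children the answers will come from caregivers who know the arm. Uniform questioning therefore reduces arm-dependent reporting but cannot remove it.

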9.3 Reporting Procedures

9.3.1 Expedited Reporting

The only research-related procedures in this protocol are finger-prick and venous blood sampling, indwelling intravenous catheterization, IV administration of AS, and oAC administration. The risk of these procedures is minimal and is generally confined to the time at which they are performed. It is expected that all patients will complete these procedures within 48 h. All unanticipated problems, related SAEs, and any protocol violations that occur between 0 and 168 h, will be reported to the NIAID IRB and USTTB EC within 7 days of PI awareness.

9.3.2 Annual Reporting

The following items will be reported to the NIAID IRB at the time of Continuing Review:

- All unanticipated problems (including AEs and non-AEs)
- Expected SAEs that are possibly, probably, or definitely related to the research
- SAEs that are not related to the research
- All protocol deviations that the investigator believes should be reported
- Any trends or events that the investigator believes should be reported

10 DATA AND SAFETY MONITORING PLAN

The NIH and USTTB PIs will monitor protocol data that could affect patient safety or confidentiality, including occurrence of AEs, documentation of patient evaluation, treatment, and disposition, and coding of patient data and samples.

11 DATA MANAGEMENT PLAN

The PI is responsible for assuring that the data collected is complete, accurate, and recorded in a timely manner. CRFs may be used as source documents for some information. CRFs will be completed and signed by study personnel, stored in folders while in use, and maintained in locked file cabinets on site during the transmission season. CRF data will be entered

electronically into Datafax© within 2 weeks of a study visit. Free-form data (e.g., physician comments) will be entered manually. Electronically-captured and manually-entered data will be checked by an on-site study manager and verified by an off-site data manager. After two-tiered validation, data will be exported to a password-protected relational-database program (Access©) and stored on a secure server. Data from this study will be prepared for presentation at scientific meetings and publication in peer-reviewed scientific journals. Under no circumstances will a patient's identity or identifying characteristics be revealed.

